- HCP Checklist for the risks of phototoxicity, SCC of the skin and hepatic toxicity: This is the core RM tool that reminds HCPs about: i) the risks of phototoxicity, SCC of the skin, and hepatic toxicity with the use of voriconazole, ii) the appropriate use of voriconazole and management of patients with underlying hepatic impairment and those developing hepatic injury during voriconazole therapy as described in the SPC, iii) the dermatological examination and liver function monitoring required per the SPC, iv) discussing the importance of monitoring these risks with patients, and, v) providing the Patient Alert Card (described below) to each patient prescribed voriconazole. The HCPs have been instructed to complete the HCP Checklist for all new patients receiving voriconazole and retain it in the patient's medical record.
- HCP Q&A Brochure for the risks of phototoxicity, SCC of the skin and hepatic toxicity: This brochure in Q&A format provides detailed information to HCPs about: i) the risks of phototoxicity, ii) counselling patients regarding the risks of hepatotoxicity and SCC of the skin, iii) alerting patients/caregivers to the signs and symptoms that warrant contacting the doctor immediately, iv) regular dermatological examination and liver function monitoring as described in the SPC, v) discontinuing voriconazole if premalignant lesions or SCC are identified; and, vi) providing the Patient Alert Card to patients prescribed voriconazole. This brochure also provides information about the HCP Checklist and Patient Alert Card and instructs HCPs how to use these tools when managing patients receiving voriconazole.
- Patient Alert Card for the risks of phototoxicity and SCC of the skin: The purpose of this wallet-sized folded card is to help remind patients about the need for dermatological evaluations on a regular basis (if phototoxic reactions occur). It also prompts the patient to report phototoxic symptoms that increase the risk of SCC of the skin. Furthermore, patients are reminded to avoid exposure to sunlight, to use protective clothing and sunscreen with high sun protective factor (SPF), and to inform their physicians if they develop sunburn or severe skin reactions or skin abnormalities. The HCPs were instructed to fill in their contact details on the card and give a card to each patient undergoing treatment with voriconazole.

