9.3. Variables

Screening questions

- Consent to participate.
- Whether the HCP managed patient(s) treated with voriconazole during the last 12 months period preceding the survey.
- Employment by Pfizer or any research organization/vendor contracted by Pfizer to administer the survey.
- Participation in qualitative research of the VFEND (voriconazole) Risk Minimisation materials.

HCP demographics and medical background

- 1. Location
- 2. Primary medical specialty
- 3. Length of professional practice as a HCP

HCP knowledge on voriconazole toxicities:

- 1. Knowledge testing for specific risks associated with voriconazole treatment
- 2. Knowledge of treatment discontinuation recommendations and dealing with toxicities

RM tools receipt

- 1. Acknowledge receiving Q&A brochure
- 2. Acknowledge receiving HCP checklist
- 3. Acknowledge receiving Patient alert card

RM tools reading

- 1. Acknowledge reading Q&A brochure
- 2. Acknowledge reading HCP checklist
- 3. Acknowledge reading Patient alert card

RM tools utilization

- 1. Frequency of using HCP checklist, Q&A brochure, and Patient alert card
- 2. Ranking the usefulness of each RM tool

Practice-related questions and, Self-declared behavior

- 1. Patient counseling
- 2. Discussing risks with patients
- 3. Liver function monitoring
- 4. Dermatological evaluation
- 5. Treatment discontinuation recommendations

Other variables

- 1. Requesting extra RM tools
- 2. Number of patients treated with voriconazole in the past 12 months
- 3. Downloading the tools from website

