Phototoxicity (eg, skin rash)			
Intestinal perforation			
Squamous cell carcinoma (SCC) of the skin			
Asthma			
Hepatic toxicity			
Cardiomyopathy			

8. Please select only one response for each statement about VFEND (voriconazole) below:

	True	False	I Don't Know
Long-term treatment (>6 months) with VFEND (voriconazole) should be considered only if the benefits outweigh the potential risks			
If phototoxic reactions occur, multidisciplinary advice should be sought and the patient should be referred to a dermatologist			
VFEND (voriconazole) should not be discontinued if premalignant skin lesions or skin Squamous Cell Carcinoma are identified			
Laboratory evaluation of hepatic function (specifically AST and ALT) at initiation and during the first month of treatment with VFEND (voriconazole) is not necessary			
If the Liver Function Tests become markedly elevated, VFEND (voriconazole) should be discontinued , unless the medical judgment of the risk-benefit balance of the treatment for the patient justifies continued use			

9.		you or your hospital receive the VFEND (voriconazole) Healthcare Professional P) Q&A Brochure?
		Yes
		No [GO TO Q10]
		I don't remember receiving it [GO TO Q10]
DISP	LAY '	THE FOLLOWING IMAGE ON THE SAME PAGE NEXT TO Q9]
		VFEND®(Voriconazole) Oral/Intravenous Healthcare Professional Question & Answer Brochure
		NFIDENTIAL Version 2, December 2022 SAU-0064 Page 2
9.1.	Did :	you read the VFEND (voriconazole) HCP Q&A Brochure ?
		Yes, all of it
		Yes, some of it
		No, I did not read it
		I don't remember reading it
		Redacted

Page 39 of 53

Voriconazole A1501110 NON-INTERVENTIONAL STUDY PROTOCOL Version 1.0, 16 August 2024

10.	Did you or your hospital receive copies of the VFEND (voriconazole) Healthcare
	Professional (HCP) Checklist?

Yes
No [GO TO Q11]
I don't remember receiving it [GO TO Q11]

|DISPLAY THE FOLLOWING IMAGE ON THE SAME PAGE NEXT TO Q10

VFEND® (Voriconazole) Healthcare Professional Checklist

Please complete this Checklist at each visit with your patient being treated with VFEND® (Voriconazole). Each of the three sections includes important risk information followed by a series of check boxes to help in the management of your patient for whom you prescribed VFEND.

A) Minimizing the Risk of Phototoxicity and Skin Squamous Cell Carcinoma

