- VFEND has been associated with phototoxicity and pseudoporphyria. It is recommended that all patients, including children, avoid exposure to direct sunlight during VFEND treatment and use measures such as protective clothing and sufficient sunscreen with high sun protection factor (SPF).
- The frequency of phototoxicity reactions is higher in the paediatric population. As an evolution towards SCC has been reported, stringent measures for the photoprotection are warranted in this population of patients. In children experiencing photoaging injuries such as lentigines or ephelides, sun avoidance and dermatologic follow-up are recommended even after treatment discontinuation.
- Squamous cell carcinoma (SCC) of the skin has been reported in patients taking VFEND, some of whom have reported prior phototoxic reactions.
- If phototoxic reactions occur, multidisciplinary advice (e.g. a consultation with a dermatologist) should be sought
 for the patient. VFEND discontinuation and use of alternative antifungal agents should be considered.
- Dermatologic evaluation should be performed on a regular basis whenever VFEND is continued, despite
 occurrence of phototoxicity-related lesions to allow early detection and management of premalignant lesions.
- VFEND should be discontinued if premalignant skin lesions or skin SCC are identified.
- SCC has been reported in relation with long-term VFEND treatment. Treatment duration should be as short as
 possible. Long- term exposure (treatment or prophylaxis) greater than 180 days (6 months) requires
 careful assessment of the benefit risk balance and physicians should therefore consider the need to limit
 the exposure to VFEND.
- For prophylaxis use, dose adjustments are not recommended in the case of lack of efficacy or treatment-related
 adverse events. In the case of treatment-related adverse events, discontinuation of VFEND and use of
 alternative antifungal agents must be considered.

Refer to the Summary of Product Characteristics for full prescribing and adverse event information.

Please review and answer the questions below for each patient receiving	og VEEND:
△ Has your patient developed phototoxicity? If YES, please refer to the Summary of Product Characteristics (SmP	YES NO
△ Have you arranged regular dermatologic evaluation for the patient presented with phototoxicity? If YES, please refer to the SmPC for further details. If NO, regular dermatologic evaluation should be arranged promptl details.	

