Knowledge about the RM tools	Q7. According to the SPC/PI, the known risks for VFEND (voriconazole) are as follows: (Please select only one response for each of the risks listed in the table below.) Q8. Please select only one response for each statement about VFEND	Yes	Question completed correctly (6 points) Question completed correctly (5 points)	An HCP is considered successful for Knowledge when he/she provides at least 9 out of 11 (~80%) correct/desirable responses. Success for
Self-declared behavior/ Practice	(voriconazole) below: Q18. Which precautionary measures do you communicate to your patients for whom you	Yes	Question completed desirably (6 points)	Knowledge: if ≥80% of HCPs are successful An HCP is considered successful for awareness when he/she provides
	prescribe VFEND (voriconazole)? Please check all that apply. 18.a Do you, or another member of your healthcare team (e.g., nurse, pharmacist or other) perform each of these activities when initiating treatment with VFEND (voriconazole)? (Please check one response for each activity below).	Yes	Question completed desirably (6 points)	desirable responses to all sub-questions. Success for self-reported practices if ≥80% of HCPs are successful
	Q19. How frequently do you perform Liver Function Tests (specifically AST, ALT)?	Yes	Question completed desirably (Answer 1 is desirable)	

Q20. If there are no changes in Liver Function Tests (LFTs) after one month of initiation of VFEND (voriconazole), how often do you monitor liver function during VFEND treatment maintenance?	Yes	Question completed desirably (Answer 2 is desirable)	
Q21. How often do you perform a dermatologic evaluation when VFEND (voriconazole) is continuously used despite the occurrence of phototoxicity related lesions?	Yes	Question completed desirably (Answer 4 is desirable)	
Q22. For which of below condition(s) would you discontinue VFEND (voriconazole) in a patient? (Select the one best response).	Yes	Question completed desirably (Answer 4 is desirable)	

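### Q22 credits only the all-of-the-above answer and has no option for the split the Checklist makes: stop for SCC or premalignant lesions, consider stopping for phototoxicity

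*Protocol*

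**What the plan says.** Q22 (protocol, Annex 1.2) asks for which conditions the HCP "would you discontinue VFEND (voriconazole) in a patient? (Select the one best response". The four options are phototoxicity, SCC, premalignant lesions, and all of these. Annex 1.5 treats only the fourth as desirable. An HCP succeeds on practice only if every practice sub-question is answered desirably, and the objective is met if at least 80% of HCPs succeed. Section 9.9.2 says every question must be answered for the survey to be completed. Q22 has no don't-know option.

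The protocol describes the discontinuation message in these places:

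- **Checklist image at Q10, SCC and premalignant lesions:** "VFEND should be discontinued if premalignant skin lesions or skin SCC are identified".
- **Checklist image, phototoxic reactions:** "VFEND discontinuation and use of alternative antifungal agents should be considered".
- **Checklist image, treatment-related adverse events in prophylaxis:** stopping and "alternative antifungal agents must be considered".
- **Checklist image, continued use after phototoxicity-related lesions:** "Dermatologic evaluation should be performed on a regular basis whenever VFEND is continued".
- **Section 7, summary of the Q&A Brochure:** "discontinuing voriconazole if premalignant lesions or SCC are identified", with no mention of stopping for phototoxicity.
- **Q8, skin statement on discontinuation:** it concerns only what to do "if premalignant skin lesions or skin Squamous Cell Carcinoma are identified".

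Section 9.3 lists "treatment discontinuation recommendations" under knowledge, and again as the fifth of the five practice variables.

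**The concern.** The programme teaches two rules of different strength. SCC and premalignant lesions call for stopping. Phototoxicity calls for considering a stop, with dermatologic follow-up if treatment goes on. Q22 puts all three conditions under one verb and takes a single choice, so it cannot record the taught rule.

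Two things are at stake. First, an HCP whose practice follows the Checklist may name a single condition for want of a matching option and so fail the whole practice objective on that item. Second, among those who choose Answer 4, the data cannot separate an HCP who would consider stopping for phototoxicity from one who would always stop.

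No other scored practice item fills the gap. Q8 covers the SCC and premalignant stop but is scored under knowledge. Q21 asks only about dermatologic evaluation when treatment continues.

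**Working it through.** The protocol gives no figure to reproduce here. The check compares the options with the Checklist and then traces the scoring rule.

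**Step 1. Options against the Checklist.** The Checklist split is: SCC, stop; premalignant lesions, stop; phototoxicity, consider stopping.

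| Q22 option | Covers SCC stop | Covers premalignant stop | Phototoxicity | Scored |
|---|---|---|---|---|
| 1. Phototoxicity | no | no | would stop | not desirable |
| 2. SCC | yes | no | not named | not desirable |
| 3. Premalignant lesions | no | yes | not named | not desirable |
| 4. All three | yes | yes | would stop, unqualified | desirable |

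Three of the 4 options omit at least one of the two required stops. One covers both but adds an unqualified stop for phototoxicity. None of the 4 matches the split.

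**Step 2. Consistency inside the survey.** The Checklist tick-boxes repeat the split: for phototoxicity they ask whether stopping was considered, and for premalignant lesions or SCC whether treatment was stopped. Q21, the question just before Q22, presupposes that treatment can continue after phototoxicity-related lesions.

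**Step 3. Weight of one item.** Annex 1.5 gives Q18 6 points and Q18a 6 points, and Q19 to Q22 count one each: 6 + 6 + 4 = 16 scored practice items. For an HCP not shown the Patient Alert Card row of Q18a the count is 15. All must be desirable, so one Q22 miss is enough to fail. Only Q22 among these items concerns discontinuation.

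**Step 4. Effect on the objective.** The target is 10 completed surveys (Section 9.5), so 0.80 × 10 = 8 successful HCPs are needed. Suppose all ten otherwise pass:

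- two single-condition answers to Q22: 10 − 2 = 8, 8/10 = 80%, met;
- three: 10 − 3 = 7, 7/10 = 70%, not met.

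The documents give no basis for the share of HCPs who would answer this way, so no probability is attached to either outcome.

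**The case against.** The best defence is the instruction to pick the one best response. For an HCP who stops for both SCC and premalignant lesions, Answer 4 is the only option that covers both, so most would probably choose it and be credited. The stem does not say always, and it can be read as asking which conditions might lead to stopping. On that reading Answer 4 is compatible with the Checklist. Stopping for phototoxicity is not shown to be wrong either: the Checklist allows it and, in prophylaxis, requires that it be considered. The 8-of-10 arithmetic would apply to a miss on any practice item. Objective 4 is judged against the SPC, which is not in the protocol. The 80% threshold is described as subjective and is not formally tested, and Section 9.7 has results reported for each question.

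Most of this stands and limits the point. A false fail is possible but not shown to be common, and crediting an HCP who would stop for phototoxicity is not a scoring error. The defect in the item remains. If nearly everyone picks Answer 4, Q22 still does not show whether practice follows the taught distinction. Reporting the Q22 distribution cannot recover an answer that was never offered, and neither can a later analysis plan.

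**Conclusion.** The concern holds, as a minor point. Q22 and its key do not match the Checklist, the Brochure summary in Section 7, or the skin discontinuation statement in Q8: 0 of 4 options express the split, and the one credited option states more than the Checklist asks for phototoxicity. The mismatch with these materials is certain. Whether the key also departs from the SPC cannot be settled from the protocol.

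The effect on the success verdict depends on how many HCPs who follow the Checklist would name a single condition, which is unknown. With 10 surveys and no other misses, it takes three to move the practice objective from met to not met. The lost distinction between considering and always stopping affects what the report can describe, whatever that number is.

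**What to change.** Before the survey is programmed, replace Q22 with one row per condition (phototoxicity, SCC, premalignant lesions). Give each row four responses: discontinue; consider discontinuing; continue without considering discontinuation; do not know. In Annex 1.5:

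- key SCC and premalignant lesions to discontinue;
- for phototoxicity, accept either discontinue or consider discontinuing;
- score the three rows together as one item, which leaves the number of scored practice items at 16 (or 15);
- report the distribution of the phototoxicity row, so that considering and automatic stopping can be told apart;
- confirm the key against the SPC before it is fixed.

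The cost is one rewritten question and key, and two more rows for each respondent. With two accepted answers the phototoxicity row is lenient, since only continuing without considering a stop, or not knowing, would miss. Its information therefore lies in the reported distribution, not in the score.
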